2.2 SCREENING EVALUATION

The following activities will be performed only after the subject has signed the consent for study # 01C0129 on which screening activities will be performed. Assessments performed at outside facilities or on another NIH protocol within the timeframes below may also be used to determine eligibility once a patient has signed the consent.

Screening evaluation may be completed within 28 days prior to enrollment unless otherwise noted

- Confirmation of histologic or cytologic diagnosis of mesothelioma by the NCI Laboratory of Pathology. If archival tissue is unavailable or insufficient for this purpose, a fresh biopsy will be collected. This may be performed at any time prior to enrollment. Remaining tissue (fresh or archival) may be used for somatic mutational analysis.
- Medical History including prior cancer therapies, history of blood transfusions
- Physical exam including vital signs and ECOG performance status
- CT scan with contrast of chest, abdomen and/or pelvis and areas of known or suspected disease involvement; MRI may also be performed when appropriate
- FDG-PET scan

- Hematology including blood smear (See footnote in 5 in Study Calendar for detailed list of assessments)
- Biochemistry assessments (See footnote 6 in Study Calendar for detailed list of assessments)
- Coagulation (See footnote 8 in Study Calendar for detailed list of assessments)
- Serum or urine β -hCG in women of childbearing potential (within 28 days prior to enrollment and confirmed on day 1 of cycle 1)
- Urinalysis (See footnote 7 in Study Calendar for additional instructions)
- Electrocardiogram (Performed within 7 days prior to enrollment. See footnote 10 in Study Calendar for additional instructions)

2.3 **REGISTRATION PROCEDURES**

Authorized staff must register an eligible candidate with NCI Central Registration Office (CRO) within 24 hours of signing consent. A registration Eligibility Checklist from the web site (http://home.ccr.cancer.gov/intra/eligibility/welcome.htm) must be completed and sent via encrypted email to: NCI Central Registration Office [contact]. After confirmation of eligibility at Central Registration Office, CRO staff will call pharmacy to advise them of the acceptance of the patient on the protocol prior to the release of any investigational agents. Verification of Registration will be forwarded electronically via e-mail to the research team. A recorder is available during non-working hours.

2.3.1 Treatment Assignment and Randomization/Stratification Procedures

| Cohorts |
|---------|
|---------|

| Number | Name | Description |
|--------|--------------|--------------------------------------|
| 1 | Mesothelioma | Subjects with malignant mesothelioma |

Arms

| Number | Name | Description |
|--------|----------|---------------------------|
| 1 | Olaparib | Twice daily oral olaparib |

Stratifications

None.

Randomization and Arm Assignment

This is not a randomized study. Subjects in Cohort 1 will be directly assigned to Arm 1.

3 STUDY IMPLEMENTATION

3.1 STUDY DESIGN

This is a phase 2, open label, single center study of olaparib in subjects with progressive malignant mesothelioma who have previously been treated. Olaparib will be continued until disease progression or unacceptable toxicity. As indicated in section 10, subjects will be analyzed in 3 separate comparison groups according to their mutation status:

- Comparison Group 1: Patients with a germline mutation in DNA repair genes
- Comparison Group 2: Patients with *BAP1* somatic mutations
- Comparison Group 3: Patients with neither germline DNA repair mutations nor *BAP1* somatic mutations

Germline samples for mutation status analysis will be collected and stored in a CLIA certified laboratory Genetics Branch (CLIA# 21D2125203). Tissue (blocks and slides) and fresh biopsies (if collected) will be stored in the NCI Laboratory of Pathology (CLIA#21D0716664). Genetic analysis will be performed retrospectively using the ClinOmics platform.

3.2 DRUG ADMINISTRATION

Olaparib at the dose of 300 mg will be given orally continuously twice daily, with doses taken at the same times each day approximately 12 hours apart. The correct number of 100mg or 150mg tablets comprising the appropriate dose should be taken at the same times each day with approximately 240 mL of water. Doses may be taken with a light meal/snack. The olaparib tablets should be swallowed whole and not chewed, crushed, dissolved, or divided.

Olaparib will be dispensed at the start of each 21-day cycle. Per the CCR policy for selfadministered oral investigational agents (PM-8) which will be followed in this protocol, patients will be provided with a pill diary (Appendix C), instructed in its use, and asked to bring it with them to each appointment.

Patients should be given clear instructions on how and when to take their study treatment. Patients will self-administer olaparib. Study site staff will make tablet counts at regular intervals during treatment. Compliance will be assessed by the tablet count and the information will be recorded in the appropriate section of the eCRF. All patients must return their bottle(s) of olaparib at the appropriate scheduled visit, when a new bottle will be dispensed. Patients will be instructed to notify study site personnel of missed doses. Dates of missed or held doses will be recorded by the patient on their patient diary and by the site staff on the eCRF.

If a patient misses more than 50% of the doses in any given cycle, the patient will be considered inevaluable for response per sections 10.3.2 and 10.3.3 and will be removed from the study.

Patients must return all containers and any remaining tablets at the end of the study.

If vomiting occurs shortly after the olaparib tablets are swallowed, the dose should only be replaced if all of the intact tablets can be seen and counted. Should any patient enrolled on the study miss a scheduled dose, the patient will be allowed to take the scheduled dose up to a maximum of 2 hours after that scheduled dose time. If greater than 2 hours after the scheduled dose time, the missed dose should not be taken, and the patient should take their allotted dose at the next scheduled time. Subjects should avoid grapefruit juice while on study, due to P450 interactions.

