3.3 DOSE DELAYS/MODIFICATIONS

Any toxicity observed during the course of the study could be managed by interruption of the dose of study treatment or dose reductions. Repeat dose interruptions are allowed as required, for a maximum of 4 weeks on each occasion. Study treatment can be modified per Table 2. If the reduced dose of 200 mg twice daily is not tolerable, no further dose reduction is allowed and study treatment should be discontinued.

Once dose is reduced, escalation is not permitted.

Table 2: Dose levels for olaparib dose modification

| Dose Level | Olaparib tablets |
|-------------------------|--------------------|
| 1 (Starting dose level) | 300 mg twice daily |
| -1 | 250 mg twice daily |
| -2 | 200 mg twice daily |

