3.3.1 Modifications and Management of Hematologic Toxicities

3.3.1.1 Anemia

| Table 3: Dos | se Delay/Mo | odification | and Manager | nent of Anemia |
|--------------|-------------|-------------|-------------|----------------|
| | •/ | | | |

| Hemoglobin | Action to be taken |
|-----------------------------|--|
| $Hb < 9 \ but \ge 8 \ g/dL$ | Give appropriate supportive treatment and investigate causality. |
| | Investigator judgment to continue olaparib with supportive treatment (e.g. transfusion) or interrupt dose for a maximum of 4 weeks. |
| | If repeat Hb < 9 but \ge 8 g/dL, dose interrupt (for max of 4 weeks) until Hb \ge 9 g/dL and upon recovery dose reduction to 250 mg twice daily as a first step and to 200 mg twice daily as a second step may be considered. |
| Hb < 8 g/dL | Give appropriate supportive treatment (e.g. transfusion) and |
| (CTCAE Grade 3) | investigate causality. |
| | Interrupt olaparib for a maximum of 4 weeks. until improved to Hb \geq 9 g/dL. |
| | Upon recovery dose reduce to 250 mg twice daily as a first step and to 200 mg twice daily as a second step in the case of repeat Hb decrease. |

Common treatable causes of anemia (e.g., iron, vitamin B12 or folate deficiencies and hypothyroidism) should be investigated and appropriately managed. In some cases, management of anemia may require blood transfusions. For cases where patients develop prolonged hematological toxicity (\geq 2-week interruption/delay in study treatment due to CTCAE grade 3 or worse anemia and/or development of blood transfusion dependence), refer to Section 3.3.1.3 for the management of this.

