3.3.1.3 Management of Prolonged Hematological Toxicities while on Study Treatment

If a patient develops prolonged hematological toxicity such as:

- ≥2-week interruption/delay in study treatment due to CTCAE grade 3 or worse anemia and/or development of blood transfusion dependence
- ≥2-week interruption/delay in study treatment due to CTCAE grade 3 or worse neutropenia (ANC < 1000/mcL)
- ≥2-week interruption/delay in study treatment due to CTCAE grade 3 or worse thrombocytopenia and/or development of platelet transfusion dependence (Platelets < 50,000/mcL)

Check weekly differential blood counts including reticulocytes and peripheral blood smear. If any blood parameters remain clinically abnormal after 4 weeks of dose interruption, the patient should be referred to hematologist for further investigations. Bone marrow analysis and/or blood cytogenetic analysis should be considered at this stage according to standard hematological practice. Study treatment should be discontinued if blood counts do not recover to CTCAE grade 1 or better within 4 weeks of dose interruption.

Development of a confirmed myelodysplastic syndrome or other clonal blood disorder should be reported to the manufacturer as an SAE and full reports must be provided by the investigator to AstraZeneca Patient Safety. Olaparib treatment should be discontinued if patient's diagnosis of MDS and/or AML is confirmed.

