10.3 POPULATIONS FOR ANALYSES

10.3.1 Evaluable for Toxicity

All patients will be evaluable for toxicity from the time of their first treatment with olaparib.

10.3.2 Evaluable for Objective Response, Progression Free Survival and Soluble Mesothelin Levels and PFS

Only those patients who have measurable disease present at baseline, have received at least one cycle of therapy, have taken at least 50% of the doses per given cycle, and have had their disease re-evaluated will be considered evaluable for response. These patients will have their response classified according to the definitions stated below. (Note: Patients who exhibit objective disease progression prior to the end of cycle 1 will also be considered evaluable.)

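### The at-least-50%-of-doses criterion for response evaluability makes no exception for permitted holds of up to 4 weeks, so a hold longer than one 21-day cycle makes the patient inevaluable as written

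*Combined protocol and SAP*

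**What the plan says.** **Evaluability.** Section 10.3.2, whose title covers objective response, PFS and soluble mesothelin, includes only patients with measurable disease who received at least one cycle, who "have taken at least 50% of the doses per given cycle", and whose disease was re-evaluated. Patients who progress objectively before the end of cycle 1 also count. Section 10.3.3 sets the same dose requirement for non-target disease. The wording counts doses taken and does not ask why a dose was not taken.

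**Removal.** Section 3.2 states: "If a patient misses more than 50% of the doses in any given cycle, the patient will be considered inevaluable for response", and continues "per sections 10.3.2 and 10.3.3 and will be removed from the study". Item 6 of the pill diary (Appendix C) tells the patient the same.

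**Permitted holds.** Section 3.3 says: "Repeat dose interruptions are allowed as required, for a maximum of 4 weeks on each occasion". Section 3.3.2 repeats this for non-hematologic toxicity. Tables 3 and 4 apply the 4-week limit to anemia and the other cytopenias; for hemoglobin below 8 g/dL, Table 3 also gives the dose at which to resume. Section 3.3.1.3 stops treatment only when recovery fails: "Study treatment should be discontinued if blood counts do not recover to CTCAE grade 1 or better within 4 weeks of dose interruption". Sections 3.3.2.4 and 4.5.2 have treatment stopped before radiotherapy and restarted within 4 weeks if any marrow toxicity has recovered.

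**Follow-up.** Section 3.5.2 says that stopping study treatment is not withdrawal from the study, and keeps patients without progression in follow-up.

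**The concern.** The longest permitted hold, 28 days, is longer than the 21-day cycle over which the criterion is assessed. A patient can follow the protocol exactly, recover, resume olaparib and still fail the criterion. The cause is then drug toxicity, not failure to comply.

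The primary analysis is ORR in evaluable patients (sections 10.1.1 and 10.4.1), and the rule of stopping at 0-1 responses also works on patients evaluated (section 10.4.6). The criterion applies to every cycle, so on a literal reading a patient with a documented response who later has a long hold becomes inevaluable. The groups are small: at 10-12% of 30 patients, Comparison Group 1 would have 0.10 × 30 = 3 to 0.12 × 30 = 3.6 patients, so reclassifying one patient would change its estimate materially.

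**Working it through.** **The plan's own figure.** The only figure tied to this rule is the accrual ceiling of 40 in section 10.2: 30 evaluable patients, an average of 3 cycles, 10% non-compliance per cycle. 30 / 0.9³ = 41.2, and 30 × 1.1³ = 39.9, so 40 is broadly reproduced. The text calls the loss non-compliance and does not say whether holds are included.

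**Inputs.**
- Cycle length, section 3.2: "Olaparib will be dispensed at the start of each 21-day cycle".
- Frequency, section 3.2: "Olaparib at the dose of 300 mg will be given orally continuously twice daily". Hence 21 × 2 = 42 doses per cycle.
- Criterion, section 10.3.2: at least 50% taken, so at least 21 of 42. It fails when 22 or more are not taken, and 22 / 2 = 11 full days.
- Longest hold, section 3.3: 4 weeks = 28 days = 56 doses.
- Assumptions: one continuous hold, all other doses taken, and a 21-day clock that keeps running. The Study Calendar allows cycle delays of up to two weeks for schedule conflicts. No rule stops the clock for toxicity.

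**Method.** For a hold of *h* doses starting at dose position *s* (1 to 42), the first cycle loses min(*h*, 43 − *s*) doses. The next loses min(42, the remainder). The criterion fails if any cycle loses 22 or more.

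| Hold | Whole-day starts that fail (of 21) | Dose-level starts that fail (of 42) |
|---|---|---|
| 10 days | 0 | 0 |
| 11 days | 11 | 21 (50%) |
| 14 days | 14 | 27 (64%) |
| 21 days | 21 | 41 (98%) |
| 28 days | 21 | 42 (100%) |

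The 14-day row by hand: starts on days 1 to 11 leave at least 11 held days in the first cycle (11 starts). Starts on days 19, 20 and 21 put 11, 12 and 13 held days in the next (3 starts). The total is 14 of 21.

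The single 21-day exception starts with the evening dose of day 11. It costs exactly 21 of 42 doses in each of two cycles, and 50% taken still passes. Beyond 21 days there is no exception: 43 or more doses cannot be split over two cycles with 21 or fewer in each, and a hold touching three cycles takes all of the middle one. A 28-day hold costs at least 28 of 42 doses (67%) in some cycle.

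**Consequence.** The prolonged-toxicity pathway of section 3.3.1.3 begins at a 2-week interruption, a length that already fails from most start days. Below 21 days, two patients with equal holds can be classified differently only because of the cycle day on which the hold began.

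**The case against.** The strongest reply is that held doses were never meant to count. Section 3.2 speaks of missed or held doses as separate things just before it states the rule, and the rule itself uses only *misses*. Section 10.2 attributes the loss of evaluability to patient non-compliance. Section 3.5.1 lists unacceptable toxicity apart from non-compliance, and section 3.5.3 has no off-study criterion for a toxicity hold. This stands as far as removal goes. A reader might infer that a patient on a permitted hold is ordered off the study; the documents do not settle that. Section 3.3.2.4 points the other way by listing missed doses among interruptions, so the text is ambiguous. The reply does not rescue evaluability, because sections 10.3.2 and 10.3.3 count doses *taken*.

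Second, the table treats start days as interchangeable and lets the clock run. The shares are not frequencies, since holds for cytopenia would cluster at scheduled blood counts. Those fall on day 1 of each cycle and day 8 of cycle 1. From either nominal day at least 21 − 8 + 1 = 14 days of the cycle remain, so a hold of 11 days or more starting there always fails. Clustering does not remove the problem. A written clock-stopping rule would, but none exists.

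Third, radiotherapy is a minor route. Section 4.5.2 limits it to painful bony metastases present at baseline, and section 3.3.2.4 wants non-toxicity interruptions kept short.

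Fourth, a minimum-exposure criterion is a legitimate design choice. That is accepted; the fault is that this one does not say how permitted holds are treated.

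**Conclusion.** The gap is real for evaluability. As written, with a running 21-day clock, holds of 10 days or less never fail the criterion alone, holds of 11 to 21 days fail depending on their start, and holds over 21 days always fail. Such patients leave the primary ORR set and, by the title of section 10.3.2, the PFS set for a treatment-related reason.

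For removal, the finding is narrower: section 3.2 and diary item 6 do not say whether a held dose is a missed dose. If it is, they conflict with the hold-and-resume text and with follow-up under section 3.5.2.

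A reader might also infer a definite loss of patients on top of the 10% per cycle allowed for in the ceiling of 40. The documents do not support this: they give no hold frequency and do not say whether the 10% includes holds. The number affected is unknown.

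**What to change.** **Clinical text.** The sponsor should reconcile section 3.2 and diary item 6 with sections 3.3, 3.3.1 (Tables 3 and 4), 3.3.1.3, 3.3.2, 3.3.2.4, 3.5.2 and 4.5.2, so that one instruction applies to a patient on a permitted hold. Which clinical rule stands is the sponsor's decision.

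**Analysis text.** In sections 10.3.2 and 10.3.3, for evaluability only, state that:
- doses on a documented investigator-directed hold are not counted as non-compliance in the 50% criterion;
- a cycle fully on hold does not by itself make a patient inevaluable;
- at least one cycle of therapy and a disease re-evaluation are still required.

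One workable form keeps the 42 scheduled doses as denominator and counts against the patient only doses missed outside a documented hold. A fully held cycle then scores 0 of 42 missed instead of an undefined 0/0, and a mostly held cycle is not decided by the few doses left. Because section 3.2 refers to these sections when ordering removal, the wording should say that it does not decide removal.

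Report held and missed doses separately.

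**Cost.** Wording changes only; sections 3.2 and 3.3.2.4 already put missed doses, holds and their reasons in the eCRF. The small downside is that some patients with low exposure stay in the response denominator, which may slightly lower the ORR.

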3.5.2 Follow Up

By discontinuing from study treatment, the patient is not withdrawing from the study. Patients should be followed for progression (if discontinuation in the absence of progression) as per the Study Calendar.

Any patient discontinuing investigational product should be seen at 30 days post discontinuation for the evaluations outlined in the Study Calendar at the Treatment discontinuation visit. The patient's tumor status should be assessed clinically and, if appropriate, disease progression should be confirmed by radiological assessment. After discontinuation of study medication, the principal Investigator/Sub-Investigator will perform the best possible observation(s), test(s) and evaluation(s) as well as give appropriate medication and all possible measures for the safety of the patient. In addition, they will record on the eCRF the date of discontinuation, the reasons, manifestation and treatment at the time of discontinuation. Patients will be required to attend the treatment discontinuation visit. The patient should return all study medication.

After discontinuation of the study medication at any point in the study, all ongoing AEs or SAEs must be followed as directed in section 6.2.1). All new AEs and SAEs occurring during the 30 calendar days after the last dose of study medication must be reported (if SAEs, they must be reported to AstraZeneca within 24 hours as described in Section 8.2.1) and followed to resolution as above. Patients should be seen at least 30 days after discontinuing study medication to collect and / or complete AE information. For guidance on reporting adverse events to the manufacturer after the 30-day follow up period see Section 8.2.2.

Any patient who has not yet shown objective radiological disease progression at withdrawal from olaparib should continue to be followed as per RECIST as detailed in Study Calendar.

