3.5.3 Off-Study Criteria

- Completed study follow-up period
- Patient non-compliance
- Participant requests to be withdrawn from study (see section 3.5.4)

- Death
- Participant lost to follow-up
- The study is discontinued

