6.4.4 Progression-Free Survival

Progression free survival (PFS) is defined as the duration of time from start of treatment to time of progression or death, whichever occurs first. Patients that have not progressed or died will be censored at the date of the last tumor assessment.

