10.2 SAMPLE SIZE DETERMINATION

The primary objective of this pilot study is to obtain preliminary estimates of the overall response rates to olaparib in patients with malignant mesothelioma according to their individual comparison group:

- Comparison Group 1 Patients with a germline mutation in DNA repair genes (estimated at 10-12% of all patients)
- Comparison Group 2 Patients with *BAP1* somatic mutations (estimated at 50-60% of all patients)
- Comparison Group 3 Patients with neither germline DNA repair mutations nor BAP1 somatic mutations (estimated at 30-40% of all patients).

All patients will be enrolled without consideration of their mutation status, and then the results will be retrospectively categorized and evaluated by mutation type. These results will be used to determine if there are any further patients to be enrolled following an amendment taking into consideration the preliminary results obtained.

It would be desirable if overall there was at least approximately a 20% response rate. The study will initially plan to enroll 30 evaluable patients in order to estimate the overall response rate with a maximum two-sided 90% confidence interval width of +/- 16%. If the observed response rate were 15-20%, the confidence interval width overall would be approximately +/-10-15%. Thus, 30 patients are adequate for an overall assessment of response. If during the initial 20 patients evaluated, there are 0-1 responses noted, then no further patients will be enrolled as soon as this can be determined since the upper one-sided 90% confidence interval bound on 1/20 is 18.1%, which is below the approximate response rate of interest. Because accrual is proceeding rapidly on the study and continued enrollment is desirable at this time, up to 25 total patients may be enrolled (5 additional patients) while awaiting the response evaluations among the first 20 patients.

It is expected that 30 evaluable patients can be enrolled in approximately 12-18 months. As patient non-compliance with study drug dosing will prevent them from being evaluable, the accrual ceiling must be adjusted accordingly. Estimating an average of 3 cycles of study therapy and a non-compliance rate of 10% per cycle the accrual ceiling will be set at 40 patients.

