15.3 APPENDIX C - PARTICIPANT OLAPARIB PILL DIARY

Today's date

Patient Name Patient Study ID

Cycle #

INSTRUCTIONS TO THE PATIENT:

- 1. Complete one form for each cycle (21 days).
- 2. You will take olaparib tablets twice a day ~12 hours apart on every day of the cycle. You must take the tablets with a large glass of water. A light snack (biscuits/ toast) is also recommended to help reduce nausea.
- 3. The olaparib tablets should be swallowed whole and not chewed, crushed, dissolved or divided.
- 4. You should avoid drinking grapefruit juice while on study.
- 5. If you miss a scheduled dose, you may take the scheduled dose up to 2 hours after the scheduled dose time. If it is more than 2 hours after the scheduled dose time, do not take the missed dose. You should then take the next dose at the scheduled time.
- 6. If you miss more than half of the doses (21 tablets) in any cycle, we will have to remove you from the study.
- 7. Record the date, the number of tablets you took, and when you took them.
- 8. If you have any comments or notice any side effects, please record them in the Comments column.
- 9. Please bring your pill bottle and this form to your physician when you go for your next appointment.

| DAY | DATE | # Tablets and When Taken | COMMENTS (side effects or missed doses) |
|-----|------|--------------------------|---|
| 1 | | AM PM | |
| 2 | | AM PM | |
| 3 | | AM PM | |
| 4 | | AM PM | |
| 5 | | AM PM | |
| 6 | | AM PM | |

| DAY | DATE | # Tablets and When Taken | COMMENTS (side effects or missed doses) |
|-----|------|--------------------------|---|
| 7 | | AM PM | |
| 8 | | AM PM | |
| 9 | | AM PM | |
| 10 | | AM PM | |
| 11 | | AM PM | |
| 12 | | AM PM | |
| 13 | | AM PM | |
| 14 | | AM PM | |
| 15 | | AM PM | |
| 16 | | AM PM | |
| 17 | | AM PM | |
| 18 | | AM PM | |
| 19 | | AM PM | |

| DAY | DATE | # Tablets and When Taken | COMMENTS (side effects or missed doses) |
|-----|------|--------------------------|---|
| 20 | | AM PM | |
| 21 | | AM PM | |

| Patient's Signature: | D | Date: | |
|----------------------|---|-------|--|
|----------------------|---|-------|--|

The Study Team will complete this section:

- 1. Date patient started protocol treatment
- _____ 2. Date patient was removed from study therapy _____
- 3. Total number of pills taken this cycle (Days 1-21)

Physician/Nurse Signature _____

15.4 APPENDIX D – ACTIONS REQUIRED IN CASES OF LIVER BIOCHEMISTRY AND EVALUATION OF HY'S LAW

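### Section 3.2 and the pill diary take patients who miss more than half their doses off study, while section 3.5.2 and calendar footnote 15 keep every non-progressed patient on scans, so PFS dates can be lost

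*Combined protocol and SAP*

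**What the plan says.** Section 3.2 sets a dose-based trigger, "If a patient misses more than 50% of the doses in any given cycle", and gives its consequence: "the patient will be considered inevaluable for response per sections 10.3.2 and 10.3.3 and will be removed from the study". Item 6 of the pill diary (Appendix C) tells patients the same: "If you miss more than half of the doses (21 tablets) in any cycle, we will have to remove you from the study".

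The protocol separates leaving therapy from leaving the study. Non-compliance is on both lists: in section 3.5.1 as a reason to leave protocol therapy, and in section 3.5.3 as an off-study criterion, worded only as "Patient non-compliance".

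Section 3.5.2 points the other way. It states "By discontinuing from study treatment, the patient is not withdrawing from the study", and adds: "Any patient who has not yet shown objective radiological disease progression at withdrawal from olaparib should continue to be followed as per RECIST". Footnote 15 of the study calendar (section 3.4) continues scans every 6 weeks until progression and accepts scans done elsewhere. Footnote 14 adds imaging at the discontinuation visit, about 30 days after the last dose, for patients who left therapy for a reason other than progression.

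For PFS, section 6.4.4 says: "Patients that have not progressed or died will be censored at the date of the last tumor assessment". Section 10.1.2 analyses PFS in all patients combined, but the heading of section 10.3.2 places PFS under an evaluability rule that requires at least half of the doses in a cycle.

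**The concern.** For a patient who has not progressed and meets the 50% rule, section 3.2 and section 3.5.2 cannot both be followed. A site that follows section 3.2 stops scanning, and the progression date is then never observed. Section 6.4.4 censors the patient at the last scan or, if the section 10.3.2 heading governs PFS, the patient is excluded altogether.

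This is a matter of data collection before it is one of analysis. Once the scans stop, no later choice of analysis set can recover the event, and a sensitivity analysis in all treated patients is no longer possible. Kaplan-Meier estimation assumes that censored patients have the same later risk as those still followed. If poor adherence goes with faster progression, that fails and PFS looks better than it is.

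**Working it through.** **How many patients meet the rule.** Section 10.2 gives the planning figures: "Estimating an average of 3 cycles of study therapy and a non-compliance rate of 10% per cycle", 30 evaluable patients and an accrual ceiling of 40.
- Never non-compliant over 3 cycles: 0.9³ = 0.729. Non-compliant: 1 − 0.729 = 0.271.
- The plan's ceiling: 30/0.729 = 41.2, close to the stated 40. Of 40 accrued, 40 × 0.729 = 29.2 stay evaluable and 40 × 0.271 = 10.8 meet the rule.

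**How many are still event-free at removal.** Some patients progress first. Assume (not in the documents) exponential PFS with a median of 18 weeks, so λ = ln 2/18 = 0.0385 per week, and 10% removed at the end of weeks 3, 6 and 9.
- 0.100·exp(−3λ) + 0.090·exp(−6λ) + 0.081·exp(−9λ) = 0.089 + 0.071 + 0.057 = 0.218, or 8.7 of 40.

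**Effect on 24-week PFS.** Let h be the hazard ratio after removal (assumed), r the week of removal and p_r the share with that removal week (0.100, 0.090, 0.081).
- True PFS = 0.729·exp(−24λ) + Σ p_r·exp(−λr − hλ(24 − r)).
- Censored at removal: everyone at risk has hazard λ, so Kaplan-Meier tends to exp(−24λ) = 39.7% whatever h is.
- With the 30-day scan: patients count until r + 30/7 weeks. The Kaplan-Meier hazard at each time is the average over those still followed, integrated numerically to week 24.

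| h | True | Censored at removal | Overstated by | With 30-day scan | Overstated by |
|---|---|---|---|---|---|
| 1 | 39.7% | 39.7% | 0 | 39.7% | 0 |
| 1.5 | 36.5% | 39.7% | 3.2 | 38.8% | 2.3 |
| 2 | 34.3% | 39.7% | 5.4 | 37.9% | 3.6 |
| 3 | 31.6% | 39.7% | 8.1 | 36.5% | 4.9 |

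Overstatements are in percentage points, taken before rounding. A simulation of 400,000 patients under the same assumptions gave 36.6%, 34.3% and 31.8% with full follow-up at h = 1.5, 2 and 3, against 39.8 to 39.9% when censored at removal.

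**A second model.** Here PFS is observed only at 6-weekly scans, the 27.1% of removal-prone patients have the higher hazard from the start, and they are removed at the end of cycle 1, 2 or 3 with no 30-day scan. PFS at 4.2 months, with a median of 3.6 months in the other patients:

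| Hazard ratio | All followed | Censored at removal | Excluded |
|---|---|---|---|
| 1 | 44.9% | 44.8% | 44.8% |
| 1.5 | 41.1% | 44.0% | 45.1% |
| 2 | 38.5% | 43.1% | 45.2% |
| 3 | 35.3% | 41.3% | 45.0% |

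Over medians of 2 to 6 months and hazard ratios of 1.5 to 3, censoring overstates PFS by about 2 to 7 points and exclusion by about 3 to 10. Between 13% and 25% of all patients were censored because of removal.

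**Against sampling error.** The 95% half-width at 40% PFS is about 1.96·√(0.4 × 0.6/n): 17.5 points at n = 30 and 15.2 at n = 40.

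**The case against.** The strongest reply is that section 3.2 is loosely worded and means off therapy. Non-compliance is an off-therapy criterion in section 3.5.1, which leads into the follow-up of section 3.5.2, and the section 3.5.3 entry does not mention doses; it may mean refusing visits or assessments. That is a fair reading of section 3.5.3, and a reason to narrow the entry rather than delete it. It does not rescue section 3.2, which ties a dose count to leaving the study, or the diary, which tells the patient so.

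Second, the 30-day discontinuation scan captures part of what would be lost. This stands and cuts the overstatement by about 30 to 40% when the scan is done. Section 3.5 also accepts a phone call, however, and one scan is not follow-up to progression.

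Third, a reader might infer that removed patients are the sicker ones, so that PFS is certainly biased upward. The documents do not say this. A related inference is that toxicity holds trigger removal. A hold of 11 days (22 of a cycle's 42 doses) can exceed half a cycle, and one of 21 to 28 days always exceeds half of some cycle; section 3.3 allows holds of up to 4 weeks. But section 3.2 names missed and held doses separately and does not say whether held doses count. Unacceptable toxicity is an off-therapy criterion and not an off-study one.

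Fourth, PFS is a secondary endpoint in a self-described pilot, with no efficacy test on it, and the conditional bias is small beside a half-width of 15 to 18 points. This limits the severity. Unlike sampling error, though, the bias would not shrink with more patients.

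**Conclusion.** The contradiction is in the text and should be resolved. Followed as written, section 3.2 can end tumor follow-up before progression in up to about a quarter of patients. The 27% is the share meeting the rule on a planning figure, and a reader should not take it as the PFS loss: about 22% (9 of 40) are event-free at removal under the assumed 18-week median.

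The bias is conditional. At assumed hazard ratios of 1.5 to 3, 24-week PFS is overstated by about 2 to 5 points if the 30-day scan is done and about 3 to 8 if it is not. With equal hazards there is no bias, only lost precision. If the section 10.3.2 heading governs PFS, the patients are excluded instead of censored, and the second model then gave a larger overstatement. The median, the hazard ratios and the removal times are assumptions. The point concerns a secondary, estimated endpoint; the primary response rate is affected separately, through evaluability.

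**What to change.** Reconcile section 3.2, section 3.5.3 and diary item 6 with section 3.5.2:
- In section 3.2 and the diary, state that missing more than half of the doses does not by itself end tumor follow-up, and that scans continue under footnote 15 until progression, death or withdrawal of consent.
- In section 3.5.3, limit the non-compliance entry to refusal of study visits or assessments.
- In section 10.3.2, state that PFS is analysed in all treated patients, consistent with section 10.1.2. Without this, the added scans could be collected and then left out of the analysis.

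The cost is wording in three sections and the diary. A few patients keep scans that are already in the calendar, and outside scans are accepted. Whether such a patient stays on olaparib is a separate clinical matter and is not addressed here.
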